3.4.2 Efficacy Variables

3.4.2.1 Primary Efficacy Variable

The primary efficacy endpoint is the ORR, defined as the proportion of patients with a best overall response of complete response (CR) or partial response (PR) according to the Lugano criteria ([Cheson 2014](#)).

3.4.2.2 Secondary Efficacy Variables

Secondary efficacy endpoints include the following:

- Duration of response: defined as the interval from date of first observed complete or partial response per Lugano criteria ([Cheson 2014](#)) to the date of documented disease progression or death due to any cause. Dates of progression and censoring will be determined as described in [Section 4.4.6.2](#).
- Disease control rate: defined as the proportion of patients with CRs, PRs, or stable disease (SD) per Lugano criteria ([Cheson 2014](#)).
- Time to response: defined as the interval from the start of study drug treatment to the first documentation of CR or PR per Lugano criteria ([Cheson 2014](#)). Patients who do not achieve a response will be censored at the date of their last tumor assessment.
- Progression-free survival: defined as the interval from the start of study treatment to the first documented date of disease progression or death from any cause, whichever occurs first. Dates of progression and censoring will be determined as described in [Section 4.4.6.2](#).

- Overall survival: defined as the time from date of first study drug treatment to date of death, for any reason. Patients without documentation of death at the time of analysis will be censored at the date the patient was last known to be alive.

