Disease assessment – Performed at least every 2 cycles with initial assessment after Cycle 2 (may be adjusted based on Investigator discretion following discussion with Medical Monitor). Disease assessment performed using a modality appropriate for the patient's tumor (e.g., PET-CT scan, CT scans, MRI). Use a consistent modality for the same patient throughout the study. May include assessment of bone marrow (e.g., aspirate, biopsy) with cytogenetics and/or fluorescence in situ hybridization (FISH) as indicated. Disease assessment data including actual scan data and radiology reports will be submitted to the Sponsor as it becomes available for evaluation by a central radiologist reader. Investigator assessment of clinical response will be documented in the source and in Electronic Data Capture. When available, tumor tissue collected during the study should be provided to the central pathology lab.

PK sample(s) – [Blood] Collected for both valganciclovir and VRx-3996. Timepoints per [Section 6.4.1](#). Collection procedure outlined in the Study Manual for all sites. Study visits with PK assessments should occur on days that the patient will take both study drugs, VRx-3996 and valganciclovir.

Urine PK collections – At selected sites only urine will be collected for levels of VRx-3996 and its metabolites on Cycle 1 Day 1. Patients will be instructed to void urine prior to administration of study drug, then all urine will be collected as described in [Table 14](#) depending on the patient Cohort. Detailed instructions are included in the Study Manual.

Hepatitis B antigen/antibodies – [Blood] Includes surface antigen, core antibody, and surface antibody. Collection procedure outlined in the Study Manual.

Hepatitis B DNA PCR – [Blood] Collected on patients with positive hepatitis B core Ab or surface Ag.

Hepatitis C antibodies – [Blood] Collection procedure outlined in Study Manual. Any patient positive for hepatitis C Ab will be evaluated for hepatitis C circulating virus by qPCR.

Hepatitis C qPCR – [Blood] Required only for patients with evidence of hepatitis C based on serology.

Human leukocyte antigen (HLA) testing – [Blood] Determination of HLA class I and II. Collection procedure outlined in the Study Manual.

Exploratory biomarkers:

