12.2. Description of Statistical Methods

Analyses performed for this study will utilize descriptive statistics. For continuous variables, the following information will be presented by cohort and study phase: n, mean, standard deviation, median, minimum, and maximum. Baseline will be the last observation prior to treatment. For categorical variables counts and percentages will be used.

The clinical outcomes of primary interest are overall response rate (ORR: complete or partial response) and duration of response (DoR). Efficacy will be presented as the percentage of patients with CRs, PRs, and SD. ORR will be calculated as CR + PR; disease control rate will be calculated as CR + PR + SD. Response criteria will follow the recommendations of Cheson et al., 2014.²⁸ The analysis of study data will be based on patient data from both the dose escalation (Phase 1b) and dose expansion (Phase 2 and Tablet cohort) parts up to the time when: i) all Phase 1b patients have completed at least 12 months of follow-up from their first disease response assessment after 2 cycles of therapy or have discontinued from the study, and ii) all patients have been followed for DoR for a maximum period of 12 months from the first dose of study medication, have died, withdrawn consent, discontinued, or are lost to follow up, whichever occurs first. The additional data for any patients continuing to receive study drugs or remaining in safety or survival follow-up beyond the final cutoff point will be summarized in a final Clinical Study Report.

The ORR and CR rates will be summarized by cohort and study phase with exact 95% confidence Intervals (CIs).

Duration of response is defined as time from date of first observed complete or partial response to the date of disease progression, death due to any cause, or last adequate (radiographic) response assessment. The DoR will be estimated for the RP2D dose patients using Kaplan-Meier estimates where patients still on treatment after 12 months will be censored.

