3. INVESTIGATIONAL PLAN

3.1 Overall Study Design

This is an open-label, 2-part, Phase 1b/2 study of nanatinostat and valganciclovir for the treatment of patients with relapsed/refractory, pathologically confirmed EBV–positive (EBV⁺) lymphoid malignancies or lymphoproliferative diseases regardless of histologic subtype.

The study will be conducted at approximately 30 sites in the US and Brazil. Written informed consent in a language fully comprehensible to the prospective patient will be obtained from each patient prior to performing any study-related procedures.

The Phase 1b portion of the study will evaluate safety and define an RP2D using a modified 3+3 design for oncology studies in patients with EBV⁺ lymphomas ([Section 3.1.1](#)). The Phase 2 portion of the study will evaluate the RP2D in patients with EBV-associated lymphomas or lymphoproliferative disease, using a Simon’s 2-stage design to allow for early stopping for futility ([Section 3.1.2](#)). The study defines a cycle length as 28 days.

Safety assessments will make use of all available data including using adverse event, clinical laboratory parameters, vital signs, electrocardiograms (ECGs), physical exams, and performance status (PS) assessments.

Response will be assessed locally using a combination of physical exam and imaging (e.g. PET-CT scan, CT scan, MRI, bone marrow/aspirate) as appropriate for each patient. Response assessments will be performed at least every two cycles, with an initial assessment after Cycle 2, using imaging modalities appropriate for the patients’ specific lymphoma based on the Recommendations for Initial Evaluation, Staging, and Response Assessment of Hodgkin and Non-Hodgkin Lymphoma: the Lugano Classification ([Cheson et al., 2014](#)).

A PK assessment of both nanatinostat and valganciclovir will be performed predose, at various timepoints following the first administration of nanatinostat/valganciclovir, and at additional timepoints within the first two cycles for all patients. A detailed schedule

that describes the coordination of PK sampling and ECGs is provided in Table 14 of the clinical study protocol.

Survival and follow-up assessments will be conducted at least every 3 months for assessment of additional therapy, response status, and survival following the safety follow-up assessment.

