4.2 Analysis Sets

The analysis sets are defined as follows:

- Intent-to-Treat (ITT) Set: The ITT includes all enrolled patients.
- Safety Analysis Set: includes all enrolled patients who receive at least one dose of nanatinostat.
- Efficacy Evaluable Set: includes all patients with measurable/evaluable disease at screening who have met all eligibility criteria and have at least one evaluable post-baseline efficacy tumor assessment.
- Pharmacokinetic Analysis Set: includes all patients in the ITT who have received at least one post-dose PK sample obtained and analyzed (i.e. valid result being

available). The PK Analysis Set is used for tabulation of nanatinostat and ganciclovir concentrations from PK plasma samples.

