4.6.3 Secondary Endpoint Analysis Methods

Disease control rate will be analyzed using the same statistical methodologies as applied to the primary efficacy endpoint in [Section 4.6.2](#).

Time to response, DoR, PFS, and OS will be summarized in days using Kaplan-Meier (KM) methodology. The number of patients who experienced the event of interest and the number of patients censored will be presented; as will KM product limit estimates of the median with associated CIs (where estimable) using Greenwood's formula. The range for all patients, as well as those who experience the event of interest will also be summarized. Kaplan-Meier estimates of the survival distribution function for DoR, PFS, and OS over time will be generated for all patients receiving study treatment. All derived efficacy measures will also be provided in a separate listing. A swimmer plot of each patient's overall tumor response assessment by EBV+ lymphoma subtype will also be presented. A listing will be provided that lists each patient's lymphoma subtype, response category, and percentage of EBER-ISH positive tumor cells.

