4.6.5.2 Handling of Dropouts or Missing Data

Best overall response is based on those patients with available data (baseline and post-baseline response assessment). Non-evaluable patients are considered non-responders and will be included in the denominator. Progression-free survival and DoR will be right-censored for patients who met one of the following conditions: 1) non-protocol systemic anti-cancer treatment started before documentation of disease progression or death, 2) death or disease progression after more than one missed disease assessment visit, or 3) alive and does not have documentation of disease progression before a data analysis cutoff date. These conventions are based on the FDA Guidance for Industry, *Clinical Trial Endpoints for the Approval of Cancer Drugs and Biologics* (2018). The analysis of PFS and DoR will be right-censored according to the conventions described in [Table 4](#).

Table 4 Conventions for Censoring for PFS and DoR

Situation	Date of Progression or Censoring	Outcome
New anti-cancer therapy started before documentation of PD or death	Date of last disease assessment prior to start of new anti-cancer therapy	Censored
Death or PD immediately after more than one consecutively missed disease assessment visit	Date of last disease assessment visit without documentation of PD that is before the first missed visit	Censored
Alive and without PD documentation	Date of last disease assessment	Censored
Death or PD between planned disease assessments	Date of death or first disease assessment showing PD, whichever occurs first	Progressed
Death before first disease assessment	Date of death	Progressed

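### Disease control rate counts stable disease from one early off-schedule or End of Treatment scan, because no earliest qualifying day is set

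*SAP*

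**What the plan says.** **Definition.** SAP 3.4.2.2: "Disease control rate: defined as the proportion of patients with CRs, PRs, or stable disease (SD) per Lugano criteria". Protocol 12.2: "disease control rate will be calculated as CR + PR + SD". Neither gives a minimum duration, an earliest qualifying day or a confirmation rule for stable disease (SD).

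**Method and analysis set.** SAP 4.6.3: "Disease control rate will be analyzed using the same statistical methodologies as applied to the primary efficacy endpoint". That means best overall response with an exact Clopper-Pearson interval, and no timing rule is added. Membership of the Efficacy Evaluable Set (SAP 4.2) requires, among other things, that patients "have at least one evaluable post-baseline efficacy tumor assessment", on any day. SAP 4.6.5.2 uses whatever baseline and post-baseline assessments are available. It also says that non-evaluable patients stay in the denominator as non-responders.

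**Timing of scans.** The notes to Table 15 in Protocol 7 say of these scans: "Performed at least every 2 cycles with initial assessment after Cycle 2 (may be adjusted based on Investigator discretion following discussion with Medical Monitor". SAP 3.1: "The study defines a cycle length as 28 days". The notes to Protocol Table 15 allow 3 days either side of a planned date. Table 15 marks a disease assessment in the End of Treatment (ET) column, and Protocol 6.3.1 ties that visit to the decision to stop VRx-3996, whenever it is made. A note to the same table says that ET assessments, where needed, match the Safety Follow-Up Visit, whose column has no disease assessment.

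**The concern.** SD means no material change from entry, so how much it says about treatment depends on how long it has lasted. At the scheduled post-Cycle 2 scan it represents about 8 weeks without progression. At a scan in week 3 it may say little beyond the baseline scan.

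Under the present rules both count equally. Suppose a patient stops for toxicity on Day 18 and has an ET scan on Day 21 with no change. That patient is in the Efficacy Evaluable Set (if otherwise eligible), has SD as best overall response, and counts as controlled with no later information. If the patient is alive without documented progression, SAP Table 4 censors progression-free survival at that same scan. One observation is a success for one endpoint and uninformative for the other.

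A patient who leaves just as early without a scan is outside the Efficacy Evaluable Set and, in Phase 2, may be replaced (Protocol 3.18; SAP 3.1.2). What is at stake is the meaning of a named secondary endpoint reported with a confidence interval. It would mix week-3 and week-8 stability without showing the mixture.

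**Working it through.** The documents state no disease control figure to reproduce. Their only design figures concern the response rate, and these reproduce. With 0 of 10 as the stopping rule, 0.95^10 = 0.5987 (stated 59.9%). With more than 3 responses in 29 as the final cut-off (inferred, not stated), type I error is 0.0468 and power 0.801. None of them involves SD.

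1. **Floor for patients scanned on schedule.** Two cycles of 28 days are 56 days, so the first scheduled scan is about Day 57. Less the 3-day window, it is about Day 54. SD at that scan already means about 8 weeks.

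2. **Effect of one early-only SD patient.** The gain is 1/N. For Phase 2, 1/30 = 3.3 points. Illustration with 12 patients otherwise controlled:

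| Early-only SD patients counted | DCR | Exact 95% CI |
|---|---|---|
| 0 | 12/30 = 40.0% | 22.7% to 59.4% |
| 3 | 15/30 = 50.0% | 31.3% to 68.7% |

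   SAP 4.1.1 also reports by cohort. In a cohort of about 10 (tablets), one such patient is worth 1/10 = 10 points.

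3. **Chance of being unchanged without drug effect.** The documents give no progression times, so these are assumptions.
   - Log-normal time to progression, log-SD 0.8, medians 6, 8 and 10 weeks: progression-free at week 3 is 80%, 89% and 93%; at week 8 it is 36%, 50% and 61%.
   - Exponential, S(t) = 0.5^(t/median), medians 1.5 to 6 months: 73% to 92% at Day 21, and 43% to 81% at Day 56.

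4. **Fall in DCR under the proposed rule**, which scores early-only SD as not controlled. Let e be the share of patients with only an early scan (also assumed). The fall is e × P(unchanged at the early scan).
   - Log-normal: 0.10 × 0.80 = 0.080 up to 0.20 × 0.93 = 0.186, so about 8 to 19 points.
   - Exponential: 7 to 9 points at e = 10%, and 15 to 19 points at e = 20%.
   - At e = 0 the fall is 0.

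5. **How conservative the proposed rule is.** Take the 8-week median and e = 20%. If everyone were read at week 8, DCR would be 50%. The present rule gives 0.80 × 50% + 0.20 × 89% = 57.8%. The proposed rule gives 0.80 × 50% = 40%. The present rule lies above that benchmark and the proposed rule below it, so both figures should be shown.

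**The case against.** The schedule already supplies most of the floor, and the provision for moving the first scan requires discussion with the Medical Monitor and does not say that the scan will be earlier. The ET scan is not clearly mandated either, because the Table 15 note conflicts with the mark in the ET column. No document gives the share of patients with only an early scan. DCR is not among the listed objectives and has no test or sample-size role; progression-free survival, the swimmer plot and the listings would let a careful reader spot a one-scan SD. A hard cut at Day 54 would also fail a stable patient whose only scan was moved slightly earlier by agreement or under the COVID-19 provisions (Protocol 18.2).

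All of this stands, and it limits the priority and calls for a sensitivity analysis. It does not supply the missing rule. SD is defined by reference to the Lugano criteria; whether that source sets a minimum interval could not be checked, and the plan states none.

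Three stronger readings are tempting but not supported. A reader might infer that the passage of time raises DCR; in fact the share still stable falls with time, and it is early scanning that raises the rate. A reader might infer that early failures in general inflate it; only leavers with an early evaluable scan do, since those without one are not counted as controlled. A reader might take the week-3 versus week-8 difference (about 4 to 8 points at a 10% to 20% early-only share and an 8-week median) as the effect of the fix; that compares the same patients at two times, whereas the fix removes them from the numerator altogether.

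**Conclusion.** The gap is real but narrow. One early unchanged scan is enough for disease control under SAP 3.4.2.2 and Protocol 12.2. The certain part of the size is 3.3 points per such patient at N = 30. The total depends on how many there are, which the documents do not give, and is zero if all scans are on schedule. The 8 to 19 points rests on an assumed 10% to 20% early-only share and assumed progression times; a smaller share gives less. The documents do not support extending the point to overall response rate, complete or partial response, or the Simon rule. As DCR is descriptive, the change is optional.

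**What to change.** In SAP 3.4.2.2, state that SD counts toward DCR only if documented at or after the first scheduled (post-Cycle 2) assessment, less the Protocol's 3-day window, that is from about Day 54. Classify SD seen only before then as not evaluable for DCR. State that these patients stay in the Efficacy Evaluable Set and in the denominator, consistent with SAP 4.6.5.2, so that the label does not remove them.

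Because this scores early-only SD as not controlled, also report the number of such patients and DCR under the present SAP definition as a sensitivity analysis. Separately, reconcile the Table 15 mark for disease assessment at ET with the note that equates ET with the Safety Follow-Up Visit.

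The cost is a short addition to the SAP and one extra table row. The downside is that the headline DCR falls by the share of patients with early-only SD.

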12.4.2. Time to Response, PFS, and OS

- Time to response (TTR): defined as the interval from the start of study drug treatment to the first documentation of CR or PR
- Progression free survival (PFS): defined as the interval from the start of study treatment to the first documented date of disease progression or death from any cause, whichever occurs first.
- Overall survival (OS): defined as the time from date of first study drug treatment to date of death, for any reason.

Kaplan Meier statistics will be used to display TTR, PFS and OS.

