4.6 Efficacy Evaluation

4.6.1 Datasets Analyzed

All efficacy summaries will be based on the EES. A data listing of patients excluded from the EES, to include the reason for exclusion, will be presented.

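### Kaplan-Meier time to response censors patients who progress or die without responding, so it can overstate the proportion responding, and its median is not the responders' median

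*SAP*

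**What the plan says.** SAP 3.4.2.2 sets the endpoint: "Time to response: defined as the interval from the start of study drug treatment to the first documentation of CR or PR per Lugano criteria". It adds one rule for everyone else: "Patients who do not achieve a response will be censored at the date of their last tumor assessment". The rule does not separate patients who have progressed or died from those still being followed.

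SAP 4.6.3 gives the estimator: "Time to response, DoR, PFS, and OS will be summarized in days using Kaplan-Meier (KM) methodology". The output is the number with the event, the number censored, and a product-limit median with confidence interval where estimable. It also states: "The range for all patients, as well as those who experience the event of interest will also be summarized". The survival functions it lists leave TTR out: "Kaplan-Meier estimates of the survival distribution function for DoR, PFS, and OS over time will be generated for all patients receiving study treatment". A TTR display comes only from Protocol 12.4.2: "Kaplan Meier statistics will be used to display TTR, PFS and OS".

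The detailed censoring table in SAP 4.6.5.2 does not reach TTR: "The analysis of PFS and DoR will be right-censored according to the conventions described in" that table, which covers only those two endpoints. No section treats progression or death as a competing event for TTR. The population is set in SAP 4.6.1: "All efficacy summaries will be based on the EES", the Efficacy Evaluable Set, which requires at least one evaluable post-baseline assessment (SAP 4.2).

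**The concern.** Kaplan-Meier is valid when censored patients have the same future event rate as those who remain at risk. A non-responder's last scan is often the last because the patient progressed, died or stopped treatment, so this censoring carries information about response. Taking such patients out of the risk set gives their share of the probability to patients who stayed, and these include the later responders.

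Two outputs suffer. One minus the KM estimate (1−KM) describes response as if progression and death did not remove anyone, so it can sit above the ORR from the same patients. The KM median mixes how many respond with how fast they do so. It may be inestimable when responders responded quickly, or be reached when fewer than half of the patients ever respond. TTR is a named secondary objective, and the study is descriptive throughout, so the reported estimates are themselves the result.

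**Working it through.** **Plan's own figures.** The documents state none for TTR. The only design figures are those of the Simon design. With 10 patients in stage 1, 29 in total and success at 4 or more responses (the cut-off is inferred, not stated), the stopping probability is 0.95^10 = 0.5987, the type I error 0.0468 and the power 0.8011. These match the stated 59.9%, 0.0468 and nominal 80%, and do not involve TTR.

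**Inputs from the documents.** Phase 2 size of 30 and target response rate of 20% (SAP 4.8). Scans at least every two cycles, the first after Cycle 2 (SAP 3.1). A 28-day cycle, hence 2 × 28 = 56 days between scans. Assessment window of ±3 days (Protocol Section 7).

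**Assumptions.** The documents do not say how responses and last scans are spread over time, so several splits are shown. Every non-responder is taken to leave through progression or death, so cumulative incidence ends at responders/N.

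**Formulas.** At scan j, d_j patients respond out of n_j at risk.
- SAP rule: 1−KM = 1 − ∏(1 − d_j/n_j).
- Cumulative incidence (Aalen-Johansen): Σ S_(j−1) · d_j/n_j, where S_(j−1) is the proportion so far without response, progression or death.

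Both use the same d_j/n_j. The KM weight does not shrink when a patient progresses or dies and S does, so 1−KM is never the smaller.

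**Fixed examples, N = 30.**

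| Responders by scan | Non-responders by last scan | 1−KM | Cumulative incidence |
|---|---|---|---|
| 6 / 0 / 0 | 16 / 5 / 3 | 1 − 24/30 = 20.0% | 20% |
| 4 / 2 / 0 | 16 / 5 / 3 | 1 − (26/30)(8/10) = 30.7% | 20% |
| 3 / 2 / 1 | 16 / 5 / 3 | 1 − (27/30)(9/11)(3/4) = 44.8% | 20% |
| 8 / 3 / 1 | 12 / 4 / 2 | 1 − (22/30)(7/10)(2/3) = 65.8% | 40% |

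Check of row two: 30 − 4 − 16 = 10 remain at scan 2. Cumulative incidence is 4/30 + (10/30)(2/10) = 20%.

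In the last row the KM survival estimate is (22/30)(7/10) = 0.513 after scan 2 and 0.342 after scan 3, so the KM median is 3 × 56 = 168 days. Eight of the 12 responders responded at day 56, so their own median is 56 days. In the first three rows 1−KM stays below 50% and no KM median exists.

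**Simulation** (4,000 trials of 30 patients, up to six scans; all per-scan probabilities assumed).

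| Response per scan (%) | Progression or death per scan | Scan dates | Mean responding | Mean final 1−KM | KM median reached |
|---|---|---|---|---|---|
| 15/8/5/5/5/5 | 50% | exact | 19% | 31% | 14% of trials |
| same | 50% | ±3 days | 19% | 40% | 26% |
| 30/15/8/5/3/3 | 40% | exact | 36% | 49% | 44% |
| same | 40% | ±3 days | 36% | 59% | 68% |
| 20, then none | 50% | exact | 20% | 20% | under 1% |
| same | 50% | ±3 days | 20% | 27% | 2% |

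The window adds to the gap because non-responders scanned a few days early leave the risk set before responders scanned a few days later.

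**The case against.** The strongest reply concerns size and reach.

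- **Size.** A reader might infer that the bias must be large and that TTR is bound to contradict the ORR. The documents do not support this, since they give neither a progression rate nor response timing. Protocol 1.11 calls these lymphomas often aggressive, which makes early exits plausible but does not measure them. Striking figures can be had by holding the response probability constant: at 20% response and 40% progression per scan, the sixth scan shows 33% truly responding against a 1−KM of 1 − 0.8^6 = 74%. But only 30 × 0.4^5 = 0.3 patients are then expected at risk, so such a figure should not be relied on. If all responses come on one day, before any non-responder is censored, the bias is zero.
- **Curve.** A reader might infer that the SAP plans a TTR curve. Its list of survival functions omits TTR, so in the SAP the exposure is the KM median and its interval.
- **Safeguards.** SAP 4.6.3 already plans event and censoring counts, the range among responders, a swimmer plot and a listing of derived measures. A careful reader can see who responded. The responders' median is still missing.
- **Wording.** Not every progressed patient is unable to respond, because treatment may continue until a repeat scan confirms progression (SAP 3.1.2). Deaths before any scan fall outside the Efficacy Evaluable Set. Both points narrow the group affected without removing it.
- **Weight.** TTR is one secondary endpoint in a single-arm study with no planned hypothesis test, and it drives no decision. That is a reason for a modest grade, not for leaving the rule as it is.

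**Conclusion.** The point holds. The direction of the error follows from the censoring rule and needs no assumption. The size does need assumptions: the illustrated gap at a 20% response rate runs from none to about 25 percentage points (44.8% − 20.0%), and it is about 26 points (65.8% − 40.0%) in the 40% example. It grows with later responses, earlier progression or death, and spread in scan dates. At the 20% target rate, the three fixed splits give no KM median, so the plan would then report no typical TTR at all. Where a KM median does appear, it can differ greatly from that of the responders (168 against 56 days in the 40% example). ORR, the Simon design and the sample size are untouched. The change should be made, but it is not critical to the trial's main conclusion.

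**What to change.** In SAP 3.4.2.2 and 4.6.3, replace the KM median TTR and its interval with a descriptive summary among responders: n, median, minimum and maximum. The range is already planned, so only the median is new.

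If an all-patient estimate or curve is shown, use the cumulative incidence of first CR or PR, with progression or death without response as a competing event (Aalen-Johansen). Non-responders still under follow-up stay censored at the last assessment. State whether a response after a first, unconfirmed progression reading counts, using the same rule as for best overall response. With complete follow-up the curve then ends at the ORR.

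Align Protocol 12.4.2, or record the departure in SAP 4.9.

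The cost is a few sentences and minor programming, with no new data. The sponsor may also have to show a less favourable figure.
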